To Compare Free Gingival Grafts and Connective Tissue Grafts Around Implants With Lack of Keratinized Mucosa

Study Protocol & Statistical Analysis Plan

NCT03338686

April 15, 2020

[name], MS, Principal Investigator
University of Alabama at Birmingham
Birmingham, AL 35294

A Prospective, Randomized Clinical Trial to Compare Free Gingival Graft and Connective Tissue Graft around Implants with a Lack of Keratinized Mucosa

Study Protocol

1. Objectives/Specific Aims:

The purpose of this study is to compare two commonly used soft tissue grafting techniques (FGG and CTG + gingivoplasty) to create/augment the soft tissue around dental implants with a lack of keratinized mucosa and to quantify the WKM gains at 6 and 12 months following incorporation at the recipient sites.

Secondary outcomes include evaluating the efficacy of gingivoplasty to induce keratinization, capturing changes in tissue thickness (tissue biotype), assessing esthetic outcomes using a newly developed peri-implant esthetic scale (PIES), and measuring patient-centered outcomes (pain, bleeding, swelling, patient satisfaction and change in daily activities) between the 2 groups. *Null hypothesis*: there will be a statistically significant difference between FGG and CTG + gingivoplasty when used to increase WKM around dental implants at 6 and 12 months post-op.

2. Materials and Method:

Study population

A total of 30 patients seeking treatment at the UAB SOD Graduate Periodontology clinics will be recruited to participate in this study according to the criteria in Table 1.

If deemed eligible, study visits, objectives, risks and benefits will be explained to all participants and IRB-approved written informed consent will be obtained. Conventional oral impressions will be made to fabricate a customized acrylic stent for reproducibility of clinical measurements. One trained calibrated examiner will be available for all study visits when clinical measurements are required. Photographs will be taken during all visits using a SLR digital camera in a 1:1 ratio.

Randomization

Randomization will take place on the day of surgery via sealed envelopes indicating the surgical approach the patient will receive, as follows:

Treatment Group 1: Free Gingival Graft (FGG)

Treatment Group 2: Connective Tissue Graft (CTG) + Laser Gingivolplasty (LG)

Table 1. Study Inclusion and Exclusion Criteria

Inclusion Criteria	Exclusion Criteria
Patients:	Systemic conditions contraindicating oral surgical procedures or adversely affecting wound healing Crestal bone loss extending apical to first implant thread Presence of peri-implantitis, acute infection and/or suppuration at the implant placement site(s)
One or more adjacent dental implants having WKM <2mm around the buccal aspect. [if there are multiple affected adjacent implants, they will all be treated but only 1 implant with the least WKM will be included in the analysis]	Presence of soft tissue recession exposing threads at implant site
Timing of intervention: Implants with healing abutments awaiting restoration or after delivery of temporary/permanent restoration	Absence of buccal plate of bone
Periodontally healthy neighboring teeth, healthy implants or edentulous ridge on either side of the involved site (s)	Previous soft tissue grafting at the implant site(s)

Surgical Visit

Group 1: Under local anesthesia, the implant site (s) will be prepared with a trapezoidal split-thickness flap on buccal aspect leaving a thin periosteum as recipient bed. Mesio-distal and apico-coronal dimensions will be measured at recipient site and a FGG with equal dimensions and uniform thickness will be harvested from the patient's palate. Exact FGG dimensions will be measured with a UNC-15 periodontal probe and its thickness will be measured using a caliper prior to placement at recipient site. FGG will be secured in position with multiple suture techniques. KM will then be measured immediately after FGG is secured. Donor site will be treated with wet gauze compression or placement of hemostatic agent if needed, and a prepared acrylic palatal stent will be delivered.

Group 2: A similar procedure will be performed with the following differences. The flap at the recipient site will be full-thickness in design. CTG harvesting from the patient's palate will be completed using a single incision or trap door technique leaving a minimal wound. After CTG is secured with sutures, the full-thickness flap will be repositioned to achieve complete CTG coverage.

Figure 1 illustrates the treatment of two implants with lack of KM using FGG.

[figure not shown]

Fig. 1. Implants with KM=0 (left)-note inflamed mucosa around implants. Creation of an adequate zone of KM 3 months following treatment with FGG (right)-note increase in tissue thickness and absence of inflammation signs

Follow-up Visits and Clinical Outcomes

The surgical sites will be examined at 1 and 2 weeks after surgical visits and loose sutures will be removed. Exams will then be scheduled at 1, 3, 6, and 12 months post-op. For participants in Group 2 (CTG), a CO2 Laser gingivoplasty will be performed at 1-month follow-up taking in account the CTG dimensions and flap thickness at time of grafting in order to expose underlying CTG to induce formation of keratinized epithelium.

The clinical parameters and the respective timing of the measurements will be evaluated for all patients as indicated in Table 2.

Table 2. Clinical parameters and their respective timing of measurement

Clinical parameters	Timing of measurements
Probing Depth (PD) using UNC periodontal probe (in mm) using a custom acrylic	Screening, Surgery (Pre-surgical),
stent	at 3, 6 and 12 months post-op
Width of Keratinized Mucosa (KM) using UNC periodontal probe (in mm) using a	Screening, Surgery (Pre-surgical),
custom acrylic stent	at 3, 6 and 12 months post-op
Width of attached mucosa (AM) will be calculated by subtracting PD from KM	Screening, Surgery (Pre-surgical),
An) Sen/	at 3, 6 and 12 months post-op
Tissue Thickness (TT1 and TT2) of peri-implant buccal mucosa will be measured	Screening, Surgery (Pre-surgical),
during the surgical visit by horizontal transmucosal probing using an endodontic	at 3, 6 and 12 months post-op
reamer after local infiltration of anesthetic prior to surgical site preparation. TT1	
and TT2 will be measured at 2 mm and 5 mm from the mucosal margin,	
respectively, using a custom acrylic stent	
Plaque Index (PI) according to Silness & Löe (1964) ¹⁷	Screening, Surgery (Pre-surgical),
	at 1, 3, 6 and 12 months post-op

Esthetic Outcomes

A newly developed peri-implant esthetic scale (PIES) will be used by a second trained calibrated examiner to objectively evaluate standardized clinical photographs taken at 6-months and 1-year after soft tissue grafting. Transparency, blending, recession/level of soft-tissue margin, gingival color, and muco-gingival junction alignment will be recorded and compared.

Patient-centered outcomes

A customized visual analog scale (VAS) will be completed by patients at 1 week (both groups) and 5 weeks post-op (CTG+LG group only) using a scale of 1 through 10: 1-having the least pain/bleeding/swelling/satisfaction/impact on daily activity and 10-having the most pain/bleeding/swelling/satisfaction/ impact on daily activity.

Statistical Analysis

The non-inferiority design of the current study operates on an assumed standard deviation (SD) of .9 and a minimally clinically significant value (d) of 1 (1mm), based on previous studies of a similar nature. Based on these values, if there is truly no difference between the standard and experimental treatment, then N=26 patients are required to be 80% sure that the lower limit of a one-sided 97.5% confidence interval will be above the non-inferiority limit of –d.

Since the results will not follow a normal distribution, a Mann-Whitney U test will be used to compare the gains in KM around dental implants between the control (FGG) and test group (CTG+LP) at 6 months and 12 months post-operatively.

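### The secondary aim claims to assess the efficacy of gingivoplasty, but no CTG patient goes without the laser and no KM reading is scheduled just before it

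*Combined protocol and SAP*

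**What the plan says.** Section 1 (Objectives/Specific Aims) sets the main purpose as comparing FGG with CTG plus gingivoplasty on width of keratinized mucosa at 6 and 12 months. It then names a separate secondary outcome: "evaluating the efficacy of gingivoplasty to induce keratinization".

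The Randomization section gives two arms, FGG and CTG plus laser gingivoplasty. At surgery in Group 2, "the full-thickness flap will be repositioned to achieve complete CTG coverage". Under Follow-up Visits and Clinical Outcomes, exams are scheduled "at 1, 3, 6, and 12 months post-op", and for Group 2 "a CO2 Laser gingivoplasty will be performed at 1-month follow-up", the purpose being "to expose underlying CTG to induce formation of keratinized epithelium".

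The Table 2 row for "Width of Keratinized Mucosa (KM) using UNC periodontal probe (in mm) using a" custom stent lists screening, pre-surgery, and 3, 6 and 12 months. Plaque Index is the only parameter in that table with a 1-month entry. Outside Table 2, the Surgical Visit section adds for Group 1 that "KM will then be measured immediately after FGG is secured". Group 2 is introduced with "A similar procedure will be performed with the following differences", which leaves open whether that reading applies there too.

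Statistical Analysis specifies one test, a Mann-Whitney comparison of KM gain between the two groups at 6 and 12 months. No analysis is given for the gingivoplasty aim.

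**The concern.** To speak of the efficacy of the laser, one needs either patients who had the same graft without it, or at least a measurement just before it. The plan has neither. The aim names gingivoplasty alone, whereas the data describe a two-stage procedure of graft, a month of healing, laser and further healing.

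What is at stake is one secondary conclusion. A KM gain in Group 2 measured from surgery could be reported as produced by the laser when part of it may have arisen in the first month, before the laser was used. The main comparison is not at risk, because it treats graft plus laser as a single procedure.

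**Working it through.** **The plan's own figure.** The only sample size in the document is for the non-inferiority comparison. With SD 0.9 mm, margin 1 mm, one-sided 2.5%, 80% power and equal allocation (assumed, since no ratio is stated), n per arm = 2 × [0.9 × (1.960 + 0.842) / 1]² = 12.7, rounded up to 13, or 26 in total. This reproduces the stated N. It sizes the comparison of whole procedures and does not bear on the laser's separate effect.

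**Which contrasts the plan offers for the laser.**

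1. *Between arms.* FGG and CTG plus laser differ in graft type, in flap design (split-thickness against full-thickness) and in the laser. The difference in KM gain reflects all three.
2. *Within Group 2.* Let A be the KM change from surgery to 1 month, and B the change from 1 month to a later visit. The schedule yields only A + B. B in turn equals the laser effect plus B0, the change that covered CTG would have shown over the same period without the laser. Reading A + B as the laser effect needs both A = 0 and B0 = 0.
   - A 1-month reading would separate A from B and so test whether A = 0.
   - B0 can be seen only in CTG patients who are not lasered, and there are none.

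**Timing.** Of the 5 parameters in Table 2, 1 (Plaque Index) is scheduled at 1 month. The first KM value in Table 2 after surgery is at 3 months, so a surgery-to-3-month change spans about 1 month before the laser and 3 − 1 = 2 months after it.

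**Other possible pre-laser references.**

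- The reading taken once the graft is secured, even if it extends to Group 2, is from the day of surgery and precedes the laser by about a month.
- Photographs are taken at all visits (Study population), but their only stated outcome use is the esthetic score at 6 months and 1 year. No KM reading from them is planned.

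**What an added 1-month reading would deliver.** The half-width of a 95% interval for the mean post-laser change is t(0.975, n − 1) × SD / √n.

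| Group 2 size | t | SD 0.6 mm | SD 0.9 mm | SD 1.2 mm |
|---|---|---|---|---|
| 15 (half of 30) | 2.1448 | 0.33 | 0.50 | 0.66 |
| 13 (half of 26) | 2.1788 | 0.36 | 0.54 | 0.73 |

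For example, 2.1448 × 0.9 / √15 = 0.498 mm. The documents give no SD for a 1-month-to-follow-up change. The 0.9 is borrowed from the sample size statement, and 0.6 to 1.2 is an assumed range. The t interval is approximate, since the plan expects non-normal results. These figures describe the precision of the proposed reading, not a bias in the plan.

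**The case against.** The strongest reply is that the plan already has an approximate pre-laser reference. The CTG is meant to stay fully covered until the laser exposes it, so KM before surgery should stand in for KM at 1 month. The documents give no reason to expect a change while the graft is covered, and the size of any change is unknown and may be negligible. This stands as a rationale. But it is an assumption about a site where a full-thickness flap has been raised and repositioned, and the plan schedules no KM value to check it. It also leaves B0 untouched.

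A second reply is that the aim may simply ask whether the staged procedure produces keratinized mucosa, which KM at 3, 6 and 12 months would answer. That reading is possible, but it repeats the main purpose, which already covers CTG plus gingivoplasty. If it is what was meant, rewording loses nothing.

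Third, the plan prescribes no before-after calculation for the laser, so misreporting is hypothetical. That is true, but with no analysis specified for the aim, nothing guards against it.

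Fourth, every probed or probing-derived parameter skips 1 month, which may be deliberate. The text gives no such reason, and both the Plaque Index exam and the laser take place at that visit.

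Finally, a 1-month reading does not isolate the laser. That is correct, which is why the wording of the aim matters more than the reading.

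**Conclusion.** The concern holds. As written, the plan cannot isolate the contribution of gingivoplasty, so the secondary aim is worded more strongly than the design supports. The missing comparator is the main limit, and the missing 1-month KM reading is the second.

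The problem is confined to this secondary outcome; the comparison of FGG with CTG plus gingivoplasty and its sample size are unaffected. How far a surgery-based gain would misstate the post-laser change cannot be quantified, because the documents give no figure for KM change in the first month. The conclusion rests on the arms, the laser timing and Table 2 as written, not on the assumed SDs. A change to the plan is worthwhile because it is small and lets the trial describe what happens after the laser.

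**What to change.** 1. Reword the secondary aim as a descriptive, uncontrolled before-after assessment of KM change following gingivoplasty within the CTG plus gingivoplasty procedure, and drop the word efficacy.
2. Add KM width at the 1-month visit to Table 2, using the same probe, stent and calibrated examiner, taken in Group 2 immediately before the laser. A matching reading in the FGG group is optional and for description only.
3. Report for Group 2 the KM at 3, 6 and 12 months minus the 1-month pre-laser value, with confidence intervals, and separately the change from pre-surgery to 1 month, which checks whether KM was unchanged while the graft was covered.
4. As a minor clarification, state whether the KM reading after the graft is secured also applies to Group 2.

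The cost is one reworded aim, one change to Table 2 and, by our estimate, a few minutes of non-invasive measurement at an existing visit. Treatment and sample size do not change. The downside is that the estimate stays confounded with healing after 1 month, and FGG cannot serve as a control for the laser. Only a CTG arm without the laser would isolate it, and that is not proposed for a 30-patient trial. If the 1-month visits have already passed, the rewording and a stated limitation are still possible.

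### The plan sets a 1 mm non-inferiority limit but names no interval or test that applies it; with whole-millimetre readings, one conventional choice would cut power to about a quarter

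*Combined protocol and SAP*

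**What the plan says.** The Statistical Analysis section describes a non-inferiority design with an "assumed standard deviation (SD) of .9" and a margin given as "a minimally clinically significant value (d) of 1 (1mm". For sample size it says "N=26 patients are required to be 80% sure", taking the true difference as zero. The criterion behind that figure reads "lower limit of a one-sided 97.5% confidence interval will be above the non-inferiority limit", with the limit set at -d. Success therefore means a lower limit strictly above -1 mm.

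The next paragraph expects non-normal results and says that "a Mann-Whitney U test will be used to compare the gains in KM" between the arms at 6 and 12 months. No confidence interval is named there. Nothing is said about ties, or about a limit that falls exactly on -1 mm.

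Table 2 (Follow-up Visits and Clinical Outcomes) lists "Width of Keratinized Mucosa (KM) using UNC periodontal probe (in mm" through a custom stent. It gives the instrument and the unit but not the reading resolution or the number of readings. The Study population section plans to recruit 30 patients. No allocation ratio is given; 1:1 is assumed below.

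**The concern.** A Mann-Whitney test as written asks whether the two distributions of gain differ. It does not produce a lower limit to hold against -1 mm, so whoever runs the analysis must choose the step that links the test to the margin. The natural choice for someone committed to Mann-Whitney is the Hodges-Lehmann interval, whose limits are order statistics of all between-patient differences in gain.

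That choice can interact badly with the measurement. If KM is recorded in whole millimetres, every gain, every between-patient difference and hence the lower limit is a whole number. The margin of 1 mm sits exactly on that grid. A limit strictly above -1 must then be 0 or higher, so the working margin becomes 0 mm. If a limit equal to -1 is accepted, the rule becomes far too lenient. At stake is whether CTG plus laser gingivoplasty, if truly equal to FGG, would be declared non-inferior about a quarter of the time or nearly always, depending on a convention the plan does not state.

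**Working it through.** **Inputs.** From the Statistical Analysis section: SD 0.9 mm, margin 1 mm, one-sided 97.5% limit, power 80%, true difference 0, N = 26. From Study population: 30 recruited. Assumed: 1:1 allocation; whole-mm recording, with 0.5 mm as the alternative.

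**The plan's own figure.** n per arm = 2 × (1.960 + 0.8416)² × 0.81 / 1² = 12.7, so 13 per arm and N = 26. This reproduces. Normal-approximation power at 13 per arm is 80.9%; with a t interval it is 77.6%. The figure belongs to a difference in means on continuous data, not to a rank method.

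**Rounding.** Rounding to 1 mm adds about 1/12 mm² of variance per reading, and a gain uses two readings, so it adds 1/6 = 0.167 mm². If 0.9 excludes rounding, the recorded SD is √(0.81 + 0.167) = 0.99. If 0.9 already includes it, the underlying SD is about 0.80, since √(0.64 + 0.167) = 0.90. The documents do not say which applies, so each range below spans both.

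**Simulation.** Baseline KM uniform on 0 to 2 mm; gain normal with mean 2.5 mm and underlying SD 0.90 or 0.80; both readings rounded; at least 8,000 trials per scenario. The Hodges-Lehmann lower limit is the 46th smallest of 13 × 13 = 169 differences, or the 65th smallest of 15 × 15 = 225. The table gives the probability of declaring non-inferiority at true difference 0.

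| Data and decision rule | 13 per arm | 15 per arm |
|---|---|---|
| Unrounded, SD 0.9, t interval | about 77% | about 83% |
| Unrounded, SD 0.9, Hodges-Lehmann limit | about 73% | about 80% |
| Whole mm, Hodges-Lehmann, limit strictly above -1 | 22–26% | 26–30% |
| Whole mm, Hodges-Lehmann, limit of -1 accepted | 95–98% | 97–99% |
| Whole mm, t interval | 69–78% | 75–85% |
| Whole mm, Mann-Whitney shifted by 1 mm, tie-corrected | 67–76% | 73–83% |
| 0.5 mm, Hodges-Lehmann, limit strictly above -1 | 47–56% | 54–64% |
| 0.5 mm, t interval | 75–84% | not needed here |

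The shifted-test range covers versions with and without a continuity correction.

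**Type I error if a limit of -1 is accepted.** Let the test arm be truly 1 mm worse. Whole-mm data then shift by exactly 1, so a limit of -1 or more occurs as often as a limit of 0 or more did at true difference 0. That is 22% to 26% at 13 per arm, against a nominal 2.5%. Neither convention rescues the order-statistic limit on this grid.

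**Why the other rules survive.** A mean difference at 13 per arm moves in steps of 1/13 = 0.08 mm, not 1 mm. The shifted Mann-Whitney test scores a pair that differs by exactly -1 as one half. The strict order-statistic rule counts all such pairs against the test arm, and the lenient rule counts them all in its favour.

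**Sensitivity.** The whole-mm Hodges-Lehmann result changed little with mean gains from 1.5 to 3.3 mm. With skewed (gamma) gains rounded once to whole mm at 13 per arm, it gave 25%, the t interval 74% and the shifted test 73% to 74%.

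**The case against.** The strongest reply is that neither condition behind the low figure is in the documents. Table 2 states a unit, not a resolution, and an examiner may read to the half millimetre. The Statistical Analysis section never mentions a Hodges-Lehmann interval, and its 80% was calculated for a mean-based one. That is correct, and it sets the limits of the point. A reader might infer that the probe itself leaves this trial with a 1-in-4 chance of success. The documents do not support that reading: on the same whole-mm data, two other defensible rules keep about 67% to 78% at 13 per arm.

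It may also be said that a t interval fits poorly with the plan's expectation of non-normal results. That is a fair point. It is met by inverting a permutation test for the mean difference, or by the shifted Mann-Whitney test, which stays closest to the method already named.

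The 30 patients planned help too. At 15 per arm with no dropout, whole-mm data and a t interval give 75% to 85%. They do not repair the order-statistic limit, which stays at 26% to 30%.

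What remains after these replies is that the plan does not say how the margin is to be tested, and its wording points towards rank methods, where the answer depends heavily on an unstated convention.

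**Conclusion.** The point holds as a gap in specification with a potentially large consequence. The plan's success criterion and its only named test are not connected, and the reading unit is not given. Under whole-mm recording and a Hodges-Lehmann limit, both assumptions, power at 13 per arm is about 22% to 26% if the limit must exceed -1. If -1 is allowed, type I error is of the same size. The loss comes from that interval construction meeting a margin that lies on the recording grid. It is not an inevitable effect of measuring in millimetres, and N = 26 is correctly derived for the mean-based interval it assumes. The ranges rest on the simulation assumptions above and on 1:1 allocation.

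**What to change.** 1. In Statistical Analysis, state the decision rule. Base non-inferiority on the one-sided 97.5% lower limit for the difference in mean gain (t-based or by inverting a permutation test), or on a tie-corrected Mann-Whitney test of gains shifted by 1 mm. State that an order-statistic limit will not be used.
2. In Table 2, state that KM is recorded to the nearest 0.5 mm at every visit. At 13 per arm this raises t-interval power from about 69–78% to 75–84%, provided the examiner can reliably read half millimetres. It does not by itself cure the Hodges-Lehmann limit, so item 1 is needed either way. If readings have already been taken, report the resolution actually used.
3. Optionally, average two or three stent-guided readings by the same examiner. With an assumed within-site SD of 0.3 mm added to the variation above, three averaged 0.5-mm readings give about 74% to 83%, against 63% to 70% for one whole-mm reading. The size of this gain depends on that assumed SD, which the documents do not supply.

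The caliper is not a ready route to finer KM readings: in the Surgical Visit text it serves the harvested graft, where "its thickness will be measured using a caliper".

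Items 1 and 2 cost one line each and need no extra patients, visits or staff. Item 3 costs a little chair time.

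### The patient-completed VAS is collected in both arms only at week 1, about three weeks before the CTG+LG arm's laser, so the randomised patient-reported comparison covers the grafting stage and not the full CTG+LG strategy

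*Combined protocol and SAP*

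**What the plan says.** All references are to the combined protocol and SAP.

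- **1. Objectives/Specific Aims** lists among the secondary outcomes "measuring patient-centered outcomes (pain, bleeding, swelling, patient satisfaction and change in daily activities) between the 2 groups".
- **Randomization** makes the laser part of the allocated strategy: "Treatment Group 2: Connective Tissue Graft (CTG) + Laser Gingivolplasty (LG").
- **Follow-up Visits and Clinical Outcomes** gives the timing for that arm: "a CO2 Laser gingivoplasty will be performed at 1-month follow-up".
- The same section sets the visits that both arms attend: "The surgical sites will be examined at 1 and 2 weeks after surgical visits", and then "Exams will then be scheduled at 1, 3, 6, and 12 months post-op".
- **Patient-centered outcomes** says that the VAS "will be completed by patients at 1 week (both groups) and 5 weeks post-op (CTG+LG group only"), "using a scale of 1 through 10".

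No other patient-reported measure is described. Table 2 lists clinical measurements, and under Esthetic Outcomes the PIES is scored by an examiner from photographs.

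**The concern.** The objective compares two strategies, and one of them has two procedures. When the only shared form is completed, patients in the CTG+LG arm have had the graft but not the laser. After the laser only that arm is asked anything.

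A week-1 comparison therefore meets the wording of the objective for the first stage of treatment only. If it were reported as the patient-reported result of FGG against CTG+LG, it would leave out the patient's experience of the second procedure and everything after it. FGG patients would be asked about satisfaction once, a week after surgery, whereas the trial judges the tissue result at 6 and 12 months.

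**Working it through.** No figure in the plan bears on this point. The one computed figure, N=26, concerns KM gain. It reproduces with equal allocation assumed: 2 × [0.9 × (1.96 + 0.84) / 1]² ≈ 12.7, so 13 per arm and 26 in total. Nothing about the VAS enters it. The check here is one of timing.

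**Inputs.** The shared VAS is at week 1 and the one-arm VAS at week 5 (Patient-centered outcomes). The laser is at the 1-month follow-up, and shared visits are at weeks 1 and 2 and months 1, 3, 6 and 12 (Follow-up Visits and Clinical Outcomes). The plan gives no visit windows, so I take week 1 as day 7, week 5 as day 35 and 1 month as day 28 to 31, all counted from grafting.

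**Step 1: shared form to laser.** 28 − 7 = 21 days and 31 − 7 = 24 days. The shared form comes 21 to 24 days before the laser, or 3.0 to 3.4 weeks.

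**Step 2: laser to week-5 form.** 35 − 31 = 4 days and 35 − 28 = 7 days. The CTG+LG form comes 4 to 7 days after the laser. An FGG patient at week 5 would be 35 days from the last procedure.

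**Step 3: count the shared time points.**

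| | Shared visits | With a VAS in both arms |
|---|---|---|
| All post-op | 6 (weeks 1, 2; months 1, 3, 6, 12) | 1 (week 1) |
| After the laser visit | 3 (months 3, 6, 12) | 0 |

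**Step 4: what each possible comparison measures.**

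- *FGG week 1 against CTG+LG week 1:* concurrent and randomised, but before the laser. It compares the grafting stages.
- *FGG week 1 against CTG+LG week 5:* roughly matched on time since the last procedure, but not concurrent, and not specified in the plan.
- *CTG+LG week 1 against week 5:* within one arm, with no control.
- *FGG week 5 against CTG+LG week 5:* concurrent and after the laser, but the FGG scores are not collected.

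Only the first rests on randomisation at a common time, and it stops short of the laser. The day counts depend on the assumed calendar; the order of events does not.

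**The case against.** The strongest reply is that the schedule is deliberate: one form about a week after each procedure. FGG patients have no procedure at 1 month, so there is nothing for a second form to follow. If their pain, bleeding and swelling are near the floor by week 5, total burden can be approximated by setting FGG week 1 against CTG+LG week 1 plus week 5. A week-5 comparison on those items would mostly show that a procedure 4 to 7 days old is felt more than one 35 days old. The outcome is secondary, and no passage says that the week-1 result will be presented as the comparison of full strategies.

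Much of this stands. The documents do not state the procedure-based reading, but the schedule fits it, and it makes the gap smaller for pain, bleeding and swelling. It does not supply the missing comparison. The approximation relies on assumed FGG scores where measured ones could be had with a short form. It also does not serve satisfaction, which has no natural floor after healing and which FGG patients could report at any time. Impact on daily activity can likewise be reported by both arms after the laser, although a floor argument may partly apply there.

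A reader might infer three stronger things, none of which the documents support:

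- *That the trial has no between-group patient-reported comparison.* It has one, at week 1, and it is sound for the grafting stage.
- *That the schedule favours CTG+LG by hiding the burden of the laser.* The documents give no VAS means or standard deviations, so neither direction nor size can be derived, and satisfaction could move either way.
- *That the main result is compromised.* The Statistical Analysis section states that "a Mann-Whitney U test will be used to compare the gains in KM around dental implants", and that test uses no VAS data.

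The same section names no VAS analysis. That is a separate omission and adds no weight to the timing point.

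**Conclusion.** The point holds in a limited form. The planned data allow a randomised, concurrent patient-reported comparison of FGG with CTG before the laser. They do not allow one of FGG with the full CTG+LG strategy, which the secondary objective names. The gap matters most for satisfaction and daily activity. It is smaller for pain, bleeding and swelling if FGG scores are near the floor at week 5, which is my assumption and not a statement in the documents.

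Its effect on the reported result cannot be quantified from the documents. It touches a secondary outcome only, and the remedy is a cheap improvement to data collection, not a repair to the trial's main analysis.

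**What to change.** Replace the VAS timing under Patient-centered outcomes with text such as:

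> *Both groups will fill in the VAS one week and five weeks after grafting. The satisfaction and daily-activity items will be repeated in both groups at the 3-month or 6-month visit (one to be chosen in advance). Between-group comparisons are secondary and descriptive. The week-1 comparison reflects the grafting stage only. At week 5 the groups differ in time since their last procedure. Numbers of forms returned will be given by group and time point.*

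The plan lists no shared visit at week 5 and does not say how that form is collected. A remote form is enough where there is no visit; use the same mode in both groups or record the mode.

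If FGG forms after the laser can no longer be collected, limit the between-group claim to the grafting stage and report the CTG+LG week-5 scores descriptively.

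**Cost.** About 15 extra short forms at week 5 (30 patients, 30 / 2 = 15 with 1:1 allocation assumed), plus two items at a visit that both groups already attend. No procedure or visit is added. The downsides are likely floor scores for FGG burden at week 5 and unequal time since the last procedure (4 to 7 days against 35), which is why the comparison should be labelled descriptive. The later satisfaction and daily-activity items are less exposed to that imbalance.
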